#### STATEMENT OF COMPLIANCE

This document is a protocol for a clinical research study. The study will be conducted in compliance with all stipulations of this protocol, the conditions of ethics committee approval, the NHMRC National Statement on Ethical Conduct in Human Research (2007) and the Note for Guidance on Good Clinical Practice (CPMP/ICH-135/95).

Nasal Deposition by NMM

Clinical trial  
HREC number: HREC/16/HAWKE/256

Trial protocol Version: 2.0  
Number: RT16-NMN-V01 /  
AFT-MD-01

Version 2

Date: 23 September 2016

Page: 1 of 31

## 1.0 Investigators and facilities

### 1.1 Study locations

This project will be conducted at Royal North Shore Hospital (RNSH). Recruitment of patients will occur via the RNSH.

### 1.3 Funding and resources

Project funding will be provided by the WIMR Respiratory Technology Group. AFT Pharmaceuticals will supply the Nasal Mesh Nebuliser (NMN) clinical prototype and provide technical assistance in operating and maintaining the device as well as site monitoring.

## 2.0 Introduction and background

### 2.1 Chronic Sinus Infection (CSI)

Chronic sinus infection (CSI) occurs regularly in patients with chronic rhinosinusitis. When the normal draining of sinuses is obstructed by swelling, excessive mucus, or an abnormality in the structure of the sinuses, aerobic and anaerobic bacterial ‘set-up-shop’ and establish biofilm colonies [1, 2] that are difficult to remove with current therapies. In many cases surgical intervention is required. CSI results in hyper-mucosal secretion, inflammation and severe discomfort and pain. Astonishingly, CSI affects a large percentage of the population with an estimated 1.9 million Australians being diagnosed in 2010–11 [3]. Symptoms are prevalent in 16% of the general population [4, 5], with acute sinusitis occurring in up to 4.6% of young adults [6].

**Limitation of current therapies:** There is no current marketed nasal aerosol medicine for the treatment of CSI, or an efficient device capable of specific targeting. Current non-surgical approaches to CSI treatment include the administration of bolus antibiotics, mucolytic and steroids. Administration is either conducted using nasal pumps or modified nebulisers; originally developed for ‘lung-targeting’. These approaches result in virtually no access to the target site, and thus limited therapeutic efficacy.

### 2.2 Nasal Mesh Nebuliser device

**The Nasal Mesh Nebuliser (NMN)** device has been developed by AFT Pharmaceuticals and has shown to be highly efficient at generating an aerosol of suitable size for nasal drug delivery and therefore has the potential to be used as a delivery system to treat chronic sinusitis and other nasal infections. Furthermore, previous researchers have established that a pulsed aerosol is required for efficient nasal delivery [7, 8]. It has been demonstrated that it is possible to generate a pulsed frequency ‘cloud’ suitable for para-sinus targeting using the AFT NMN. The main competitor to the AFT NMN with this capability is PARI SINUS® (PARI, Starnberg, Germany), which only achieves ca. 6.5% sinus deposition [9], has long dosing times (4 min/nostril [10]) and a high potential for lung deposition. However, the

[figure not shown]

Figure 1: Operating principle of the CSI-NMN device. In-house prototype schematic.

Nasal Deposition by NMM

Clinical trial  
HREC number: HREC/16/HAWKE/256

Trial protocol Version: 2.0  
Number: RT16-NMN-V01 /  
AFT-MD-01

Version 2

Date: 23 September 2016

Page: 7 of 31

NMN, can deliver a dose quickly (10mL/min) with a particle size suited for nasal deposition (i.e.  $\geq 10 \mu\text{m}$ ) and has the potential for a high sinus deposition. Furthermore, by varying the pulsation frequency (PF) sinus and nasal deposition may also be optimised.

The NMN (Figure 1) works on the principle of focusing ultrasonic energy via a 880 kHz transducer into a liquid formulation that is enclosed behind a thin palladium alloy film containing thousands of micron-sized holes. Cavitation within the formulation causes a ‘sonocapillary effect’ [11], essentially extruding droplets through the mesh orifices to produce a dense aerosol with particles of suitable size for nasal deposition. The device can operate over short time frames and has been designed to emit the aerosol during the patient’s exhalation, via a mouthpiece actuator (Figure 2A); avoiding any potential lung inhalation of medicament. Importantly, the pulse frequency (1-500 Hz) of the device can be adjusted easily to help control dosing to enhance sinus delivery.

[figure not shown]

Figure 2: (A) concept of final clinical device prototype (B) cumulative aerosol particle size distribution of PARI SINUS and other commercially available nebulisers vs. the NMN prototype. Purple and blue regions correspond to optimal particle sizes for lung and nasal deposition, respectively. ( $n=5 \pm \text{StDev}$ ).

**Preliminary study:** In-line laser diffraction studies, using the development-prototype NMN (Figure 2A), have shown that a narrow particle size can be achieved which is suitable for nasal drug delivery (Figure 2B). In general, the median particle diameter of isotonic saline after 3 seconds operation was  $53.9 \mu\text{m} \pm 2.6 \mu\text{m}$ . This is in comparison to  $2.75 \mu\text{m} \pm 0.15 \mu\text{m}$  for the PARI SINUS. Under these conditions, the output rate was 20x that of the PARI SINUS. Additionally, two other commercial nebulizers were tested (Omron® and AeroNeb-Go®) and it was shown that they were also not suitable for nasal deposition (Figure 2B). Subsequently, the effect of pulsation frequency (Hz) on aerosol generation and particle size using the NMN device has been investigated and shown that changing the pulse frequency had little effect on aerosol size, measured by laser diffraction (Figure 3A).

Using a commercially available silicon cast of the human upper respiratory tract (Koken LM005, Koken Ltd, Tokyo, Japan; also referred to in this study as ‘Boris’) (Figure 3B), the effects of pulsative frequency and orifice size of the mesh on nasal deposition were evaluated.

[figure not shown]

Figure 3: (A) Influence of pulse frequency at 10 and 50 Hz on aerosol particle size over a 3-second period.  $D_{0.9}$  represents diameter of 90th percentile cumulative size distribution. ( $n=5 \pm StDev$ ). (B) Assembly (left) and testing of prototype NMN (right) in nasal cast model. Yellow water sensitive coating reacts with saline and turns red upon contact. The circled region in top view highlights the maxillary sinus inlet.

Preliminary studies using the Boris model (Figure 4) indicated these particles were deposited within the nasal cavity, with no observable oral-pharynx deposition. It also demonstrated that by applying different pulsative frequencies different nasal deposition profiles could be achieved but these observations need to be confirmed *in vivo*.

[figure not shown]

Figure 4: Assembly and testing of prototype NMN in nasal cast model with different pulsative frequency: (A) no pulse frequency (continuous delivery mode) (B) 10 Hz pulse frequency, (C) 50 Hz and (D) 100 Hz. Red areas indicate saline deposition from NMN device using a water indicating gel for a delivery volume of 0.33 mL

### 2.3 Rational for current study

The proposed study aims to investigate the regional deposition in the nasal cavity of aerosols generated from the clinical NMN prototype using different pulse frequency modes. Information from this study will be used to aid in determining the optimal

deposition settings for future targeting of medication to the sinuses and within the nasal cavity.

Once beyond the nasal valve, the deposition pattern within the nasal cavity is vitally important. Deposition on middle meatus is of particular significance as this is the location of the ostiomeatal complex, a group of structures that receive drainage from the anterior and medial ethmoid cells, the frontal sinus and the maxillary sinus. Other important sites include the ostia of the sphenoid and posterior ethmoid sinuses, which are located superoposteriorly to the ostiomeatal complex on the sphenoethmoid recess and superior/supreme meatus, respectively. Improving the deposition to these regions is of clinical importance as it would translate into improved therapeutic effects in CRS, including patients that have undergone Functional Endoscopic Sinus Surgery (FESS).

To evaluate this, radio-labelled aerosols of a saline solution will be delivered using the clinical NMN prototype and sequential imaging will be performed using Single-photon emission computed tomography (SPECT) or positron emission tomography (PET) (depending on accessibility and availability of equipment in the hospital) and gamma scintigraphy imaging. Simultaneously, high resolution computed tomography (CT) scans of the nasal and sinus anatomy will be obtained from all participants and used as templates for overlaying subsequent deposition data to provide a detailed assessment of deposition characteristics.

Four different pulse frequency settings will be evaluated including: A) no pulse frequency (continuous delivery mode), B) a 10 Hz pulse frequency C) a 50 Hz pulse frequency and D) a 100 Hz pulse frequency based on preliminary *in vitro* studies and those investigated by other researchers [9].

Furthermore, the high-resolution head CT scan data from the participants will be used to generate an anatomically correct model of the upper respiratory tract that includes the sinus cavities. While there are several models of the upper respiratory tract available in the literature [12, 13] and commercially available cast models, such as the Koken LM005 silicon cast referred to as 'Boris' in our earlier studies, these models do not contain the sinus regions and are generally not suitable for routine deposition analysis to evaluate sinus delivery.

The CT scan data will enable the development of a representative nasal cast that includes sinus structure allowing for realistic *in vitro* simulation and optimization for sinus delivery in the future.

Royal North Shore Hospital has a well-established research group using 3D imaging techniques (SPECT/PET) and gamma scintigraphy imaging to assess lung physiology and regional ventilation distribution and CT to determine morphological changes in the respiratory tract with multiple published studies in the field [14-16].

The intent of the present study is to provide evidence and demonstrate that the NMN device will be able to effectively and efficiently target the sinus region of the nasal

cavity. Results from the proposed study will be intended to support the registration of the device for use with a range of currently available medicaments that targets the nose.

### 3.0 Study objectives and endpoints

#### 3.1 Study hypothesis

It is hypothesised that increasing the pulsative frequency (0-100 Hz) produced by the NMN device will improve deposition within the sinuses.

#### Statistical consideration

This is an exploratory study using a new clinical NMN prototype to determine the regional depositions in the nasal cavity of aerosols using different pulse frequency modes in healthy volunteers. It is also of interest to determine whether the new NMN prototype will achieve higher deposition (>6%) compared to previous similar clinical studies using other devices. Specifically, in a study by Moller et al [9], about 6.5% of activity deposited in the nasal cavity was detected in the sinus of five healthy volunteers using new PARI VibrENT nebulizer system.

A previous study that investigated the temporo-spatial deposition of saline delivered by a squeeze bottle, nasal saline spray and nasal gel, enrolled 5 healthy subjects [17]. Similarly, a PARI VibrENT nebulizer system that evaluated the pulsating aerosol (fixed frequency of 25 Hz) to the sinuses was conducted with five healthy volunteers [9]. Taking into account that four different pulse frequencies are evaluated, a sample size of minimum 10 subjects will be sufficient for this pilot study. It should be noted that all recruited participants will be randomised to receive radiolabelled saline generated with all four different pulse frequencies settings.

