### 4.2 Study design

This study will be performed in healthy Caucasian male participants with no history of sinusitis or chronic respiratory diseases.

Informed consent will be obtained for participants prior to the initiation of any study-specific procedures including screening. All participants will receive a head CT scan on their first visit.

The treatment sequence for the study participants will then be randomly applied with at least a 72-hours washout period between treatments (Table 1). The potential carry-over effect of the applied radiolabel is considered negligible since Technetium has a half-life of 6 hours, consequently a 'rest' minimum period of 72 hours is considered sufficient between imaging study days.

*Table 1. Treatment types to applied in the proposed study*

Treatment	Device	Application method
A	NMN	No pulsing (continuous mode)
B	NMN	10 Hz pulse
C	NMN	50 Hz pulse
D	NMN	100 Hz pulse

Each participant will receive a radio-labelled saline dose of 2.0 mL per visit by one of the application methods (Table 1), the order of which will have been randomly selected.

Nasal deposition, retention and clearance of radiolabelled saline solution will be measured using serial imaging of SPECT/PET and gamma scintigraphy. The study does not involve the use of novel treatments and is restricted to investigating the ability of the NMN device to target the paranasal sinuses.

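### The question of higher sinus deposition than other devices rests on a bare >6% cut-off and one five-volunteer figure, with no concurrent comparator, so as written it cannot support a comparative conclusion

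*Protocol*

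**What the plan says.** The Statistical consideration text under Protocol 3.1 calls the study exploratory and adds a cross-device question: "It is also of interest to determine whether the new NMN prototype will achieve higher deposition (>6%) compared to previous similar clinical studies using other". The benchmark follows: "about 6.5% of activity deposited in the nasal cavity was detected in the sinus of five healthy volunteers using new PARI VibrENT nebulizer system". The same text describes that study as one that "evaluated the pulsating aerosol (fixed frequency of 25 Hz) to the sinuses was conducted with five healthy volunteers".

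Section 2.2 cites the same reference and the same figure, but attaches them to PARI SINUS, which it presents as the main competitor: "which only achieves ca. 6.5% sinus deposition [9".

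Table 1 in 4.2 lists four treatments, all delivered by the NMN: continuous, 10 Hz, 50 Hz and 100 Hz. Each participant gets all four, one per visit: "Each participant will receive a radio-labelled saline dose of 2.0 mL per visit by one of the application methods". Section 4.3 enrols until 11 participants have completed; 3.1 and 5.1 give a minimum of 10.

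The cross-device question does not appear in the hypothesis (3.1), the primary objective and endpoint (3.2), the secondary objectives (3.3) or the specified tests (3.4). Those tests compare NMN settings with one another. The primary endpoint is an area in mm². The quantity that could be set beside 6.5% is the regional share of total nasal deposition described in 3.4.

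Section 2.3 says the study is meant to "demonstrate that the NMN device will be able to effectively and efficiently target the sinus region of the nasal" cavity, and that the results are intended to support registration of the device.

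**The concern.** A question about outperforming other devices needs either a comparator in the trial or a stated way of using an outside figure. The protocol has neither. Its only written criterion is a threshold of 6%, half a percentage point below the benchmark it is meant to beat. A device equal to the benchmark, or slightly worse at say 6.2%, would more often than not show an observed mean above 6%. The benchmark is one mean from five people, at a frequency the NMN is not tested at, and the protocol does not say which of the four NMN settings is to be held against it.

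What is at stake is a sentence in the study report, and possibly in the registration file, saying that the NMN deposits more in the sinuses than earlier devices. These data could not support that sentence. The benchmark would also be credited to different devices depending on whether 2.2 or 3.1 is read.

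**Working it through.** **Inputs from the protocol.** Threshold 6%; benchmark mean 6.5%, n = 5, no SD (3.1); four NMN settings (4.2); 11 completers (4.3). There is no planned figure to reproduce: the sample size is argued only from two earlier five-person studies and the number of frequencies, with no SD, effect size or power.

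**Assumptions.** The protocol gives no SD for the sinus share and no within-participant correlation between settings. I take a between-participant CV of 30% to 100%, or SDs of 1.5, 3 and 4.5 percentage points, and correlations of 0 to 0.9. Means are treated as normal. No advantage means a true mean of 6.5% at every setting.

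**1. One pre-chosen setting against the written 6%.** SE = CV × 6.5/√11 and P(mean > 6) = Φ(0.5/SE).
- CV 30%: SE = 1.95/3.317 = 0.588; Φ(0.850) = 0.80.
- CV 100%: SE = 6.5/3.317 = 1.960; Φ(0.255) = 0.60.

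An NMN with no advantage therefore passes 60-80% of the time. Simulation with SD 1.5, 3 and 4.5 gives 0.87, 0.71 and 0.64. Against 6.5% instead of 6% the figure is 0.50, as for any unbiased mean set against its true value.

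**2. Best of four settings, if that were the rule.** Probability that at least one observed mean exceeds the reference (simulation, n = 11, SD 3):

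| Correlation | Any > 6.5%, benchmark fixed | Any > benchmark, benchmark also varying (n = 5, same SD) | Any > 6% |
|---|---|---|---|
| 0 | 0.94 | 0.74 | 0.99 |
| 0.3 | 0.86 | 0.70 | 0.96 |
| 0.5 | 0.80 | 0.66 | 0.93 |
| 0.7 | 0.73 | 0.63 | 0.89 |
| 0.9 | 0.63 | 0.57 | 0.82 |

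Two entries in the fixed-benchmark column have exact values: 1 − 0.5⁴ = 0.9375 at correlation 0, and 1 − 1/5 = 0.80 at 0.5. The fixed- and varying-benchmark columns do not depend on the SD; the last column does.

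**3. Uncertainty of the benchmark.** With equal SDs, allowing for its n = 5 multiplies the standard error of the comparison by √((1/11 + 1/5)/(1/11)) = √(1 + 11/5) = 1.79. A 95% CI for the benchmark, 6.5 ± 2.776 × SD/√5, would be 4.6-8.4, 2.8-10.2 or 0.9-12.1 for SD 1.5, 3 or 4.5.

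**4. If a formal test were used instead.** For a one-sample t-test at two-sided 0.05, counting only results in the higher direction (n = 10 or 11):
- Against a fixed 6.5%: about 2.5% false results for one prespecified setting, and 5-10% for any of four.
- Against 6%: 9-53% for any of four.
- When the five-person mean is itself an estimate but is treated as known: 11-13% for one setting and 16-27% for any of four.

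**The case against.** The strongest reply is that the comparison carries little weight in this plan. It is a side interest in a study that calls itself exploratory, outside every listed endpoint and test. An analysis plan not seen here could name a setting and a test. This stands, and it limits the severity. An analysis plan could not, however, add a concurrent comparator, and it would still inherit a cut-off below the benchmark.

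A reader might infer that the plan picks the best of four means, so that an apparent advantage is the expected outcome when there is none. The documents do not support that. The protocol states no best-of-four rule; it only leaves the setting open. Finding the optimal frequency is the main objective (3.2), which makes the best setting a natural candidate, but that is a possibility and not the plan. The probabilities in step 2 also apply only to bare point estimates; under a formal test against 6.5% they fall to 5-10%.

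A reader might also join 2.3 to 3.1 and see a planned superiority claim for registration. Section 2.3 names no competitor. A statement on how well the NMN reaches the sinuses, given with its uncertainty, needs no comparator and would be legitimate.

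Nor is the benchmark presented as exact: the protocol writes it as approximate in both places, and 3.1 gives the five volunteers. Testing at 25 Hz would not make the comparison like-for-like, since 2.2 describes devices that also differ in particle size and output. The discrepancy in device name is editorial; whether the two names describe one device cannot be settled from the protocol.

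**Conclusion.** The point holds in limited form. The trial has no concurrent comparator for its cross-device question. The only benchmark is an approximate mean from five people without an SD, and the only criterion is a bare 6% that lies below it. Read as written, an NMN with no advantage passes at a single pre-chosen setting about 60-80% of the time (n = 11, CV 100% to 30% assumed). If the best setting were used, at least one mean would exceed a fixed 6.5% with probability 0.63-0.86 for correlations of 0.9 to 0.3. If the benchmark also varies, the range is 0.57-0.70 for the same correlations, and 0.74 at zero correlation. CV and correlation are assumptions.

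The severity is minor to moderate: no listed endpoint or specified test is affected, but the registration purpose in 2.3 makes an unsupported comparative sentence worth preventing.

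**What to change.** - **Statistical consideration (3.1):** replace the >6% criterion with a statement that the comparison with the published figure is descriptive. Report the sinus share of nasal activity with a 95% CI for all four settings, beside the published mean and its n of 5. State that no conclusion of higher deposition than other devices will be drawn from it, and in particular none from the best setting.
- **2.2 and 3.1:** reconcile the device named for the 6.5%, and give its frequency in both places.
- **2.3:** it need not be limited to differences between NMN frequencies. It should only not be used to support a comparative device claim.

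The cost is wording in 2.2 and 3.1, with no added participants, scans or data. The downside for the sponsor is a less favourable statement for the registration file.

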#### 3.2 Primary objective and endpoint

The main objective of the study is to determine the optimal frequency for the NMN that will provide the basis for future *in vivo* sinus targeting of drug delivery systems. The primary endpoint of this study is the total area of distribution (mm^2) of radiolabelled saline immediately after administration by the NMN (T0) in the different regions of the sinus cavity.

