#### Interpretation and assumption of quantitative data

The quantitative assessment of nasal deposition, retention and clearance will be determined as a percentage of total nasal deposition (quantified using the first planar image immediately after inhalation of the radioaerosol) as a function of intensity within defined areas of the nasal cavity, left and right of the maxillary, frontal, ethmoidal and sphenoidal sinuses using standard protocol as briefly described below. Count rates in the selected region of interests will be analysed using the MATLAB Software or ImageJ Software packages (<http://rsb.info.nih.gov/ij/>). Count rates will be corrected for background activity and radioactive decay.

For analysis of the distribution of the radiolabelled saline into the different compartments, all serial images will be superimposed with regions of interest (ROI) of the nasal airways and sinuses defined as shown in Figures 6 and 7. The activity is obtained in these ROIs.

[figure not shown]

Figure 6. Regions of interest of the nasal cavity of the right and left maxillary and frontal sinuses (MR, FR, FL and ML). Image was taken from [9].

The primary endpoint of this study is the total area of distribution ( $\text{mm}^2$ ) of radiolabelled saline immediately after administration by the NMM ( $T_0$ ). This will be evaluated for each of subsites (surgically expanded ostia of the paranasal sinuses and oropharynx) and compared between treatments (A-D) which correspond to the different pulse frequencies tested. Between-treatment differences in total area of deposition of radiolabelled saline at each subsite will be compared by means of one-way analysis of variance (ANOVA) with application method as a factor.

Pairwise comparisons will be performed between each of the pulsed application methods and the continuous application (no pulse). Pairwise comparisons will be tested using a two-tailed p-value of  $<0.05$ .

Clearance will be calculated by the decrement in total radiolabelled saline between  $T_0$ ,  $T_{20}$  and  $T_{60}$ . Clearance will be evaluated for each subsite and compared between treatments (A-D). As with the primary efficacy endpoint, between-treatment differences in radiolabelled clearance will be tested by means of one-way analysis of variance (ANOVA) with application method as a factor. Pair-wise comparisons will be made between each of the pulsed application methods and the continuous application (no pulse).

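### The bar for higher deposition (>6%) lies below the cited comparator's 6.5%, and the share of activity it refers to is not a named endpoint and has no stated comparison between frequencies at T0

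*Protocol*

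**What the plan says.** The hypothesis (Protocol section 3.1) is that "increasing the pulsative frequency (0-100 Hz) produced by the NMN device will improve deposition within the sinuses". It names no unit. Section 3.2 gives the objective, "The main objective of the study is to determine the optimal frequency for the NMN", and then the endpoint: "The primary endpoint of this study is the total area of distribution", in mm², immediately after administration.

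The Statistical consideration part of section 3.1 adds a second interest, to "determine whether the new NMN prototype will achieve higher deposition (>6%) compared to previous similar clinical studies using other devices". Its next sentence describes the comparator: "about 6.5% of activity deposited in the nasal cavity was detected in the sinus of five healthy volunteers". Section 2.2 repeats the figure as roughly 6.5%.

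Under Interpretation and assumption of quantitative data, section 3.4 says that deposition, retention and clearance "will be determined as a percentage of total nasal deposition". This uses intensity in regions that include the left and right sinuses, with counts corrected for background and decay. The T0 comparison stated there is on another scale: "Between-treatment differences in total area of deposition of radiolabelled saline at each subsite", by one-way ANOVA. Clearance is compared as a fall between T0, T20 and T60. Retention is compared as an AUC over 60 minutes, for area and for intensity, by ANCOVA with the T0 value as covariate.

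**The concern.** Two things do not fit together.

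First, the bar for being higher than earlier devices is lower than the result of the earlier device cited for it. A reader applying the written criterion could report an improvement where the prototype deposits less. Section 2.3 says the results are meant to support registration of the device, so a loose comparative statement could travel beyond this pilot.

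Second, the benchmark is a share of activity and the primary endpoint is an area. The share is computed but has no status: it is neither a primary nor a secondary endpoint, and the protocol states no comparison of it between the four settings at T0. The choice of frequency would then rest on how widely the saline spreads, with no planned comparison of how much reaches the sinuses at the start.

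**Working it through.** **Step 1: the benchmark against its own comparator.** Both inputs come from the Statistical consideration part of section 3.1: a bar of more than 6% and a comparator of about 6.5%.

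- Gap: 6.5 − 6.0 = 0.5 percentage points.
- Relative gap: 0.5 / 6.5 = 7.7%.

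Any mean above 6% and below 6.5% meets the bar and is lower than the comparator. This needs no assumption.

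**Step 2: how often the wrong bar would mislead (illustration).** The protocol gives no standard deviation for the sinus percentage, so I assume a between-subject SD of 1 to 4 points. I take n = 11 from the completer target in section 4.3. By the normal approximation, P(observed mean > c) = Φ((μ − c) / (SD/√n)).

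Example with SD 2: the standard error is 2/√11 = 0.603. For a true mean of 6.2%, (6.2 − 6.0)/0.603 = 0.33, giving 0.63. Against a bar of 6.5%, (6.2 − 6.5)/0.603 = −0.50, giving 0.31.

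| Assumed SD (points) | True mean 6.5%: P(mean > 6%) | True mean 6.2%: P(mean > 6%) | True mean 6.2%: P(mean > 6.5%) |
|---|---|---|---|
| 1 | 0.95 | 0.75 | 0.16 |
| 2 | 0.80 | 0.63 | 0.31 |
| 3 | 0.71 | 0.59 | 0.37 |
| 4 | 0.66 | 0.57 | 0.40 |

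With a bar of 6.5%, a device equal to the comparator would exceed it with probability 0.50. With n = 10 the picture is the same (for SD 2: 0.79, 0.62 and 0.32).

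**Step 3: precision of a mean from 11 participants.** The 95% half-width is t(0.975, 10) × SD/√11, with t = 2.228. For assumed SDs of 2, 3 and 4 points it is 1.34, 2.02 and 2.69 points. The half-point gap lies well inside that uncertainty, so the comparison needs an interval as well as the right bar.

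**Step 4: which stated comparisons address the amount deposited at T0?**

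| Comparison between frequencies (section 3.4) | Amount in the sinuses at T0? |
|---|---|
| Area (mm²) at T0, ANOVA | No: extent; the same area can carry different counts |
| Clearance, ANOVA | No: a fall from T0, not the starting level |
| AUC of area, ANCOVA | No: extent over time |
| AUC of intensity, ANCOVA adjusted for T0 | No: the T0 difference is adjusted away |

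The sinus percentage appears in section 3.4 as a way of quantifying the images, but in none of these comparisons and not among the endpoints of sections 3.2 and 3.3.

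**The case against.** The strongest reply is that area is a legitimate measure here. The hypothesis says only that pulsing "will improve deposition within the sinuses", without an amount or a share. The protocol itself speaks of an area of deposition, and section 2.3 stresses where the saline lands (middle meatus, sinus ostia), which is a rationale for coverage. This stands. A reader might infer that the primary endpoint contradicts the hypothesis and must be replaced; the documents do not support that.

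A reader might also infer that area is blind to dose. The protocol fixes no segmentation rule, and that detail can properly sit elsewhere. Under an assumed Gaussian hot spot with a cut-off at 40% of peak, doubling the activity leaves the area unchanged if the cut-off is relative, but raises it by 76% if the cut-off is a fixed count (ln 5 / ln 2.5 = 1.76). So area may or may not follow dose, and no firmer statement is warranted.

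Nor are the data for the benchmark missing: the percentage will be computed and could be set against 6.5%. The benchmark is described only as being of interest in an exploratory study. It is not a success rule, and the comparator is itself approximate. These points limit the consequence. They do not explain a bar below the cited figure, nor supply a T0 comparison of the percentage.

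Finally, one might want to demand a lower confidence limit above 6.5% before any claim. That would treat an approximate mean from five volunteers as a known constant and ignore its sampling error.

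**Conclusion.** The point holds in limited form. The bar of more than 6% is wrong against the protocol's own comparator by 0.5 points (7.7%); this is plain from the text. It is equally plain that the sinus percentage is quantified but is not an endpoint, and that no between-frequency comparison of it at T0 is stated, although the benchmark is expressed on that scale.

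The probabilities and interval widths rest on an assumed SD of 1 to 4 points and approximate normality; the ordering of 6% and 6.5% does not. Reading the hypothesis as a statement about share of activity is an inference, so area as primary is a debatable choice rather than an error. The benchmark affects neither alpha nor sample size. This is something to fix before the data are seen, but it does not invalidate the design.

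**What to change.** 1. In the Statistical consideration part of section 3.1, replace the 6% bar with about 6.5%, and state that the denominator is the same as the comparator's: activity deposited in the nasal cavity.
2. Report the mean sinus percentage for each frequency with its 95% confidence interval, as a descriptive comparison. Say that the comparator is an approximate mean from five volunteers.
3. In sections 3.2 to 3.4, name background- and decay-corrected sinus activity at T0, as a percentage of total nasal activity, as an endpoint compared between frequencies alongside area. It can be co-primary or key secondary, or primary if the sponsor cannot justify area. If it is co-primary, say how the two results are to be read together.

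The cost is wording in sections 3.1 to 3.4 and one further analysis of counts already planned. The benchmark becomes slightly harder to meet.
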